For these reasons, we have chosen to compare inhaled corticosteroids to a long-acting muscarinic antagonist and to placebo in this study of non-eosinophilic asthma.

III. HYPOTHESES TO BE TESTED IN THIS TRIAL

A. Overall Research Question

Among asthmatic participants who are persistently non-eosinophilic (<2% sputum eosinophils in two induced sputum samples collected 3-6 weeks apart), is there a preference for inhaled corticosteroids (ICS) or long-acting muscarinic antagonist (LMA) compared to placebo?

B. Co-Primary Research Questions

1. Among asthmatic participants who are persistently non-eosinophilic, is there a preference for ICS compared to placebo?

2. Among asthmatic participants who are persistently non-eosinophilic, is there a preference for LMA compared to placebo?

(For both ICS and LMA, preference to treatment is defined as the following hierarchy of outcomes: Treatment Failure = TF, then Asthma Control Days = ACD, then FEV₁)

C. Secondary Research Question

1. Does the statistical preference for each of three alternative therapies (ICS, LMA, placebo) differ in participants with the non-eosinophilic phenotype compared with participants with sputum eosinophilia?

D. Exploratory Research Questions

1. Can other, easier to obtain biomarkers (blood periostin, blood eosinophils, or eNO) be used instead of sputum eosinophils to identify patients likely to respond to ICS?

2. Among asthmatic participants who are persistently non-eosinophilic, is there a preference for ICS compared to LMA?

3. Among asthmatic participants with sputum eosinophilia, is there a preference for ICS compared to LMA?

4. When do patients with prednisone-treated exacerbations recover from the impairment associated with this event?

5. When do patients return to their pre-exacerbation state of work/school/physical activity?

E. Primary Research Hypotheses

1. Among asthmatic participants who are persistently non-eosinophilic, the preference for ICS will be greater than placebo.

2. Among asthmatic participants who are persistently non-eosinophilic, the preference for LMA will be greater than placebo.

F. Secondary Research Hypothesis

The differential response to three alternative therapies (ICS, LMA, placebo) will be different in participants with and without airway eosinophilia, as assessed by sputum eosinophils (i.e., asthmatics with airway eosinophilia [sputum eosinophils $\geq 2\%$] will prefer ICS and asthmatics who are persistently non-eosinophilic will prefer LMA).

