regimen B, then treatment regimen A is deemed to be superior to treatment regimen B and the process is terminated. If not, then continue to the next step.

2. If the SIENA participant experiences at least 31 greater annualized ACDs on treatment regimen A as compared to treatment regimen B, then treatment regimen A is deemed to be superior to treatment regimen B and the process is terminated. If not, then continue to the next step.

3. If the SIENA participant displays at least a 5% improvement in FEV₁ on treatment regimen A as compared to treatment regimen B, then treatment regimen A is deemed to be superior to treatment regimen B and the process is terminated. If not, then the two treatment regimens are deemed to be “equivalent” or “tied” for that SIENA participant.

In order to describe the primary and secondary null hypotheses, we introduced the following notation:

- $p_{Eos-,ICS>Placebo}$ = probability that ICS is superior to placebo within the non-eosinophilic phenotype
- $p_{Eos-,Placebo>ICS}$ = probability that placebo is superior to ICS within the non-eosinophilic phenotype
- $p_{Eos-,ICS\approx Placebo}$ = probability that ICS and placebo are equivalent within the non-eosinophilic phenotype = $1 - p_{Eos-,ICS>Placebo} - p_{Eos-,Placebo>ICS}$
- $p_{Eos-,LMA>Placebo}$ = probability that LMA is superior to placebo within the non-eosinophilic phenotype

- $p_{Eos-, Placebo > LMA}$ = probability that placebo is superior to LMA within the non-eosinophilic phenotype
- $p_{Eos-, LMA \approx Placebo}$ = probability that LMA and placebo are equivalent within the non-eosinophilic phenotype = $1 - p_{Eos-, LMA > Placebo} - p_{Eos-, Placebo > LMA}$
- $p_{Eos+, ICS > Placebo}$ = probability that ICS is superior to placebo within the eosinophilic phenotype
- $p_{Eos+, Placebo > ICS}$ = probability that placebo is superior to ICS within the eosinophilic phenotype
- $p_{Eos+, ICS \approx Placebo}$ = probability that ICS and placebo are equivalent within the eosinophilic phenotype = $1 - p_{Eos+, ICS > Placebo} - p_{Eos+, Placebo > ICS}$
- $p_{Eos+, LMA > Placebo}$ = probability that LMA is superior to placebo within the eosinophilic phenotype
- $p_{Eos+, Placebo > LMA}$ = probability that placebo is superior to LMA within the eosinophilic phenotype
- $p_{Eos+, LMA \approx Placebo}$ = probability that LMA and placebo are equivalent within the eosinophilic phenotype = $1 - p_{Eos+, LMA > Placebo} - p_{Eos+, Placebo > LMA}$

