The co-primary research hypotheses are that within the non-eosinophilic phenotype, ICS is superior to placebo and LMA is superior to placebo. In statistical terms, the null hypotheses are

- (1) $H_0: p_{Eos-, ICS > Placebo} = p_{Eos-, Placebo > ICS}$
- (2) $H_0: p_{Eos-, LMA > Placebo} = p_{Eos-, Placebo > LMA}$

Since $p_{Eos-,ICS \approx Placebo}$, $p_{Eos-,LMA \approx Placebo}$, $p_{Eos+,ICS \approx Placebo}$, and, $p_{Eos+,LMA \approx Placebo}$ do not factor into the null hypotheses, participants who do not have a differential response (i.e., treatment was equivalent to placebo) will not be included in the analyses. We will apply two-sided, exact binomial tests at the 0.025 significance level (Bonferroni correction) for each of these null hypotheses. To assess potential period and seasonal effects, a sensitivity analysis will be performed by applying logistic regression models to those who had a differential response (i.e., the treatments were not equivalent), with covariates to adjust for period differences, season of enrollment, and ICS delivery (DPI/MDI).

Secondary analyses with the primary outcome include the following:

1. Comparisons within the eosinophilic phenotype in terms of the null hypotheses $H_0: p_{Eos+,ICS > Placebo} = p_{Eos+,Placebo > ICS}$ and $H_0: p_{Eos+,LMA > Placebo} = p_{Eos+,Placebo > LMA}$, which we will test via two-sided, exact binomial tests at the 0.025 significance level (Bonferroni correction) for each of these null hypotheses.
2. Comparisons between the non-eosinophilic and eosinophilic phenotypes in terms of the null hypotheses $H_0: p_{Eos-,ICS > Placebo} = p_{Eos+,ICS > Placebo}$ and $H_0: p_{Eos-,LMA > Placebo} = p_{Eos+,LMA > Placebo}$, which we will test via two-sided, 0.025 significance level Fisher exact tests (Bonferroni correction).
3. Comparison of the ICS and LMA treatments in the manner described above for the primary and secondary analyses (within the non-eosinophilic

phenotype, within the eosinophilic phenotype, and between the eosinophilic and non-eosinophilic phenotypes, respectively).

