For the co-primary comparisons within the non-eosinophilic phenotype, the sample size of 262 yields statistical power of 0.9 with two-sided, 0.025 significance level tests (Bonferroni correction), while allowing for a 15% drop-out rate, to detect $p_{Eos-,ICS>Placebo} - p_{Eos-,Placebo>ICS} = 0.20$ (and to detect $p_{Eos-,LMA>Placebo} - p_{Eos-,Placebo>LMA} = 0.20$). We assume that 30% of the participants will not display a preference for ICS versus placebo and therefore not included in the primary analysis (and that 30% of the participants will not display a preference for LMA versus placebo). The following table illustrates the level of statistical power for selected sample sizes.

N	$p_{Eos-,ICS \approx Placebo}$ or $p_{Eos-,LMA \approx Placebo}$	$p_{Eos-,ICS>Placebo} - p_{Eos-,LMA>Placebo}$ or $p_{Eos-,Placebo>ICS} - p_{Eos-,Placebo>LMA}$	Statistical Power
	0.30	0.20	
202	0.30	0.20	80%
228	0.30	0.20	85%
262	0.30	0.20	90%

With respect to the secondary analysis of the primary outcome, the following table illustrates the statistical power for detecting $p_{Eos+,ICS>Placebo} = 0.71$ and $p_{Eos-,ICS>Placebo} = 0.45$, yielding a difference of 0.26 between the two phenotypes (and for detecting $p_{Eos+,LMA>Placebo} = 0.71$ and $p_{Eos-,LMA>Placebo} = 0.45$, yielding a difference of 0.26 between the two phenotypes).

EOS-Negatives		EOS-Positives			Statistical Power
N	$p_{Eos-,ICS>Placebo}$ or $p_{Eos-,LMA>Placebo}$	N	$p_{Eos+,ICS>Placebo}$ or $p_{Eos+,LMA>Placebo}$		
202	0.45	58	0.71		80%
228	0.45	66	0.71		85%
262	0.45	74	0.71		90%

For the secondary analysis of comparing the ICS and LMA treatments within the non-eosinophilic phenotype, there is 90% statistical power with a sample size of 262 to detect a difference of 0.185 ($= p_{Eos-,LMA>ICS} - p_{Eos-,ICS>LMA}$) with a two-sided, 0.05 significance level test.

H. Anticipated Results

Our primary hypothesis is that the response to ICS and LMA will be different in participants with and without airway eosinophilia. We anticipate that ICS will be more effective in asthmatics with airway eosinophilia and that LMA will be more effective in asthmatics who are persistently non-eosinophilic.

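### Does the tie exclusion in VIII.C also apply to the between-phenotype Fisher tests?

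*Combined protocol and SAP*

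**What the plan says.** VIII.C classifies each participant, for each pair of treatments, as better on one, better on the other, or tied. For each phenotype and each active treatment against placebo it defines three probabilities that sum to 1. One of them, for example, is the "probability that ICS is superior to placebo within the eosinophilic phenotype".

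After the two co-primary nulls, p(active > placebo) = p(placebo > active) in the non-eosinophilic (EOS-) phenotype, the plan names the four tie probabilities, two for each phenotype. It says that they "do not factor into the null hypotheses" and concludes that "participants who do not have a differential response (i.e., treatment was equivalent to placebo) will not be included in the analyses". The next sentence applies exact binomial tests at two-sided 0.025. A sensitivity analysis follows, "applying logistic regression models to those who had a differential response".

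The secondary analyses of the composite come next:

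- Item 1 repeats the binomial tests in the eosinophilic (EOS+) phenotype.
- Item 2 tests p(EOS-, ICS > placebo) = p(EOS+, ICS > placebo), and the same for LMA, by two-sided Fisher exact tests at 0.025. It gives no denominator.
- Item 3 is the "Comparison of the ICS and LMA treatments in the manner described above for the primary and secondary analyses".

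For the co-primary power, VIII.G assumes that 30% of participants "will not display a preference for ICS versus placebo and therefore not included in the primary analysis". For item 2 it uses 0.71 (EOS+) against 0.45 (EOS-).

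**The concern.** The exclusion is worded for the analyses in general, and it names the EOS+ tie probabilities, which appear in neither co-primary null. A literal reader could therefore carry it into items 2 and 3.

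The stated reason does not travel that far. In a within-phenotype null the tie rate cancels. In the between-phenotype null it does not: if ties are dropped, the Fisher test compares p/(1 - tie rate) in the two phenotypes, and this matches the written null only when the tie rates are equal. The plan gives a tie rate for EOS- only.

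The tests concerned are the ones that answer the secondary research question in III.C: "Does the statistical preference for each of three alternative therapies (ICS, LMA, placebo) differ in participants with the non-eosinophilic phenotype", compared with those who have sputum eosinophilia? A denominator chosen once the data are in hand would be an avoidable freedom. In the ICS v LMA version there is a further gap: with ties kept, counting ICS > LMA or LMA > ICS gives different tables, and item 3 names no direction.

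**Working it through.** **Inputs.** From VIII.G: 202, 228 or 262 EOS- with 58, 66 or 74 EOS+; EOS- ties 30%; co-primary difference 0.20; 0.71 v 0.45 between phenotypes; 15% drop-out, stated for the co-primary comparisons and assumed here for the Fisher table too. From VIII.C: two-sided alpha 0.025. The EOS+ tie rate is not given, so it is ranged.

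**1. Co-primary power, ties dropped.** Better + worse = 1 - 0.30 = 0.70 and better - worse = 0.20, so better = (0.70 + 0.20)/2 = 0.45 and worse = 0.25. Among non-ties, 0.45/0.70 = 0.643. The non-tied numbers are N x 0.85 x 0.70 = 120, 136 and 156. Exact binomial power is 0.812, 0.855 and 0.903, against the stated 80%, 85% and 90%. It reproduces.

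**2. What 0.45 means in the Fisher table.** It equals the all-participant EOS- probability in step 1. The value among non-ties would be 0.643. Read as a share of non-ties, 0.45 would mean that placebo is preferred in EOS-, which contradicts the co-primary assumption.

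**3. Fisher power for 0.45 v 0.71, by exact enumeration.** N x 0.85 gives 172 v 49, 194 v 56 and 223 v 63.

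| Denominator | Row 1 | Row 2 | Row 3 |
|---|---|---|---|
| Stated in VIII.G | 80% | 85% | 90% |
| Ties kept, doubled tail | 0.811 | 0.871 | 0.914 |
| Ties kept, probability ordering | 0.845 | 0.892 | 0.927 |
| 30% ties dropped in both phenotypes, probability ordering | 0.673 | 0.711 | 0.764 |

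With ties kept, the doubled-tail version comes within about 2 points of the stated figures. Probability ordering runs 2.7 to 4.5 points above them. No stated power is missed.

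**4. Why the reason is valid for one null and not the other.** Within a phenotype, p(A>B) = p(B>A) gives p(A>B)/[p(A>B) + p(B>A)] = 1/2 at any tie rate. Between phenotypes, dropping ties tests p(EOS-)/(1 - t(EOS-)) = p(EOS+)/(1 - t(EOS+)), where t is the tie rate.

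**5. How far the two denominators can diverge.** Fisher test, probability ordering, alpha 0.025. Ties kept: 223 v 63. Ties dropped: 156 v 63 x (1 - t), which is 57, 50, 44 and 38.

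| Assumed EOS+ tie rate t | 10% | 20% | 30% | 40% |
|---|---|---|---|---|
| p = 0.45 in both phenotypes, ties dropped | 0.32 | 0.10 | 0.02 | 0.14 |
| p = 0.45 in both phenotypes, ties kept | 0.02 | 0.02 | 0.02 | 0.02 |
| 0.643 of non-ties in both, ties kept | 0.32 | 0.08 | 0.02 | 0.08 |
| 0.643 of non-ties in both, ties dropped | 0.02 | 0.02 | 0.02 | 0.02 |

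The two pairs of rows mirror each other. Each test holds its level for its own null and rejects when the other quantity differs. At equal tie rates (30%) they agree.

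**6. What the text points to.**

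- The exclusion stands between the co-primary nulls and the sentence that applies binomial tests to them. The Fisher tests come later, in a separate list.
- The EOS+ tie terms have a natural use in item 1, which is a within-phenotype test.
- Item 2 writes its null in symbols defined over everyone in the phenotype.
- VIII.G says that tied participants are left out of the primary analysis.

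Nothing in the documents points positively to dropping ties from the Fisher tests.

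**The case for a change.** The strongest case for a change is that all of this is inference. A programmer who follows the sentence literally could drop ties everywhere, and the result could then depend on the EOS+ tie rate. Under VIII.G's own alternative, 0.71 v 0.45, ties-dropped power would be 0.08, 0.39, 0.90 and about 1.00 at assumed EOS+ tie rates of 0, 10%, 20% and 29%. With ties kept it is 0.93 (0.91 doubled tail) throughout.

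The power table is not conclusive alone. Without drop-out, some ties-dropped calculations also land near the stated row: a continuity-corrected normal approximation at alpha 0.05 gives 0.804, 0.855 and 0.901, and an unpooled one at 0.025 gives 0.820, 0.866 and 0.908. The intention-to-treat statement does not settle the matter either, since the co-primary tests fall under it and still drop ties.

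What stands is that the denominator is nowhere written down and that item 3 names no direction. The rest has less force. The rival calculations leave out drop-out, one of them uses the wrong alpha, and both read 0.45 as a share of non-ties, which contradicts the co-primary assumption. The broad reading also requires the analyst to set aside the null as written. As for item 3, III.D lists the within-phenotype ICS v LMA comparisons as exploratory, and both directions can simply be reported.

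**Conclusion.** No change is needed. The plan omits a detail that its own notation supplies: the Fisher tests compare probabilities defined over the whole phenotype, so a tie counts as not superior. An analyst who tests the null as written does this without further instruction, and the stated power agrees with it to within about 2 points (doubled tail, 15% drop-out assumed for this table).

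The differences in rejection rate, up to 0.32 against 0.02 over assumed EOS+ tie rates of 10% to 40%, show that the two denominators answer different questions. They are not type I error rates of the planned test, and they vanish when the tie rates are equal. The reason given for the exclusion is correct for the binomial tests to which it is attached. A clarifying sentence would do no harm, but it would only confirm the natural reading. The co-primary tests, the sample size and the stated power stay as they are.

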#1 or #2 will be classified as "eosinophilic" and need not undergo sputum induction #3.

G. Choice of 2% Eosinophils For Sputum Eosinophilia Cutpoint

The cutpoint of $\geq 2\%$ eosinophilis has been validated in number of small studies and 2 large studies in which the distribution of sputum eosinophils in healthy individuals has been described. Belda and colleagues from Hamilton examined 118 healthy individuals and found $0.4 \pm 1.4\%$ eosinophils ²³. In 114 healthy individuals Spanevello et al reported $0.6 \pm 0.8\%$ eosinophils, and found no healthy participant with $>2.4\%$ eosinophils ²⁴ (**Figure 10**).

V. STUDY POPULATION INCLUSION AND EXCLUSION

A. Rationale for Inclusion and Exclusion Criteria

Criteria are based on the NAEPP Classification of Asthma Severity for children \geq 12 years of age and adults. Our goal is to recruit participants with mild-moderate asthma for whom an inhaled corticosteroid would normally be the recommended treatment. Because all participants will receive no controller during the Run-In, and because we believe that the eosinophil negative participants will not respond to ICS, we have defined a Treatment Failure status that will trigger intervention. We believe that the criteria for Treatment Failure are sufficiently conservative that participants whose asthma control deteriorates will be "rescued" before they develop an exacerbation. This rescue algorithm was used successfully in the NHLBI-ACRN IMPACT study ³ - a comparison of daily versus "as-needed" ICS for mild persistent asthma. Participants who meet Treatment Failure status during the Run-in will be treated according to a rescue

algorithm and will continue in the study. If necessary, the run-in will be extended so that ≥ 3 weeks elapse after TF before randomization. To provide an additional level of safety, we have added additional exclusion criteria at the end of the Run-in that must be met before participants can be randomized. Finally, TF criteria will also be used throughout the treatment period - to ensure the safety of participants.

NAEPP Classification of Asthma Severity ≥ 12 years of age (Figure 4-6)			
	Mild	Moderate	Severe
Symptoms	> 2 days/week	Daily	Throughout day
Nighttime awakenings	3-4/month	> 1x/week	Often 7x/week
SABA use (not for EIB)	> 2 days/week	Daily	Several times/day
FEV1	> 80%	60-80%	< 60%

SIENA Inclusion, Exclusion and Treatment Failure Criteria				
	Inclusion	Exclusion Week 0	Exclusion Week 6	Treatment Failure*

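### Holm's step-down would keep the 5% family error limit that fixed 0.025 tests give the two co-primary comparisons, and add power for the second claim

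*Combined protocol and SAP*

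**What the plan says.** Section VIII.C sets out two co-primary hypotheses: "The co-primary research hypotheses are that within the non-eosinophilic phenotype, ICS is superior to placebo and LMA is superior to placebo". For the tests it says "We will apply two-sided, exact binomial tests at the 0.025 significance level (Bonferroni correction) for each of these null hypotheses". Participants with no preference between active drug and placebo are left out of each test.

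Section VIII.G sizes the trial on the same rule. It states that "the sample size of 262 yields statistical power of 0.9" for each comparison at two-sided 0.025, "while allowing for a 15% drop-out rate", with 30% of participants tied and a preference difference of 0.20 for each drug.

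Section VIII.F plans no formal interim efficacy analysis, so nothing else spends the co-primary alpha. Nowhere does the plan let alpha pass from one co-primary test to the other once the first is rejected.

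**The concern.** Each comparison stays at 0.025 whatever the other one shows. If one null hypothesis has been rejected, at most one true null remains in the family, and it could be tested at 0.05 without the family error rate exceeding 5%. The plan leaves that alpha unused.

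What is at stake is the second claim. Under the plan's rule, a second drug preferred by 92 to 64 or by 91 to 65 among 156 participants with a preference would be declared negative, although a 5% family rate would allow the claim once the first drug had succeeded.

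The value of the change depends on whether ICS works in non-eosinophilic participants, and the document points both ways. Section III.E hypothesises "Among asthmatic participants who are persistently non-eosinophilic, the preference for ICS will be greater than placebo", while V.A says "we believe that the eosinophil negative participants will not respond to ICS", and IX.B repeats that belief.

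**Working it through.** **Inputs.** From VIII.G: N = 262, 15% drop-out, 30% ties, difference 0.20. From VIII.C: two-sided exact binomial tests at 0.025, ties excluded. Assumed: the correlation between the two comparisons. Both use the same participants and the same placebo period, but the documents give no figure.

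**1. Reproduce the plan's power.**
- Evaluable: 262 × 0.85 = 222.7, about 223.
- With a preference: 222.7 × 0.70 = 155.9, about 156.
- Win and loss probabilities: (0.70 + 0.20)/2 = 0.45 and (0.70 − 0.20)/2 = 0.25. The win probability among those with a preference is 0.45/0.70 = 0.643.
- At level 0.025 the exact test rejects at 93 or more of 156. Power is 0.9025, or 0.902 when the number of ties among 223 is random.
- The other rows of the VIII.G table also reproduce: 0.801 at N = 202 (stated 80%) and 0.853 at N = 228 (stated 85%).

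**2. What level 0.05 adds to the second test.** With 156 preferences:

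| Result | Two-sided exact p | Fixed 0.025 | Holm, other hypothesis already rejected |
|---|---|---|---|
| 93 v 63 | 0.020 | reject | reject |
| 92 v 64 | 0.030 | not rejected | reject |
| 91 v 65 | 0.045 | not rejected | reject |
| 90 v 66 | 0.065 | not rejected | not rejected |

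The smallest claimable difference falls from (93 − 63)/223 = 0.135 to (91 − 65)/223 = 0.117. Allowing for random ties, exact power is 0.902 at level 0.025 and 0.943 at 0.05; exact size is 0.020 and 0.041.

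**3. Independent comparisons, by hand.** Write P1 = 0.902 and P2 = 0.943.
- Both rejected, Bonferroni: P1² = 0.814.
- Both rejected, Holm: P1² + 2·P1·(P2 − P1) = 0.814 + 2 × 0.902 × 0.041 = 0.888.
- Each drug, Holm: P1 + P1·(P2 − P1) = 0.902 + 0.902 × 0.041 = 0.939.
- At least one, either rule: 1 − (1 − 0.902)² = 0.990.

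**4. Correlated comparisons, by simulation.** Each scenario used 40,000 trials of 223 participants (80,000 for error rates in the runs at a set correlation). Latent normal variables were cut to give the stated win, loss and tie probabilities.

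Both differences 0.20:

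| Dependence (assumed) | Power per drug | Power for both | At least one |
|---|---|---|---|
| Independent | 0.90 to 0.94 | 0.81 to 0.89 | 0.99, unchanged |
| Shared placebo | 0.90 to 0.94 | 0.83 to 0.90 | 0.975, unchanged |
| Latent correlation 0.7 | 0.90 to 0.93 | 0.84 to 0.90 | 0.96, unchanged |

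In each cell the first figure is Bonferroni and the second Holm.

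LMA difference 0.20, ICS difference varied, shared placebo:

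| True ICS difference | ICS rejected, Bonferroni | ICS rejected, Holm |
|---|---|---|
| 0.20 | 0.904 | 0.935 |
| 0.15 | 0.65 | 0.73 |
| 0.10 | 0.29 | 0.39 |
| 0.05 | 0.08 | 0.12 |
| 0 (false claim) | 0.021 | 0.037 |

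Runs at latent correlations of 0 and 0.5 gave 0.64 to 0.73 for a second-drug difference of 0.15, and a false-claim rate under Holm of 0.038 to 0.040. If the ICS difference is 0, LMA power stays at 0.90.

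**5. Family error.** With both nulls true it is 0.039 to 0.040 under either rule. With one null true it is about 0.02 under Bonferroni and 0.037 to 0.040 under Holm. All are below 0.05.

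**The case against.** The strongest reply is that the plan contains no defect. The rule is prespecified and valid, the trial is sized for exactly that rule, and the sizing is right. That is correct, and keeping Bonferroni would not harm the trial's validity.

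The gain is also modest at the design point: 3 to 4 percentage points on a test that already has 90% power. VIII.G sets no target for winning on both drugs. The larger gains arise at ICS differences of 0.15 and 0.10, below the 0.20 the trial was sized to detect. This stands as a description of size. It does not show a loss, since every Bonferroni rejection is kept.

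If non-eosinophilic participants do not respond to ICS, the trade is unfavourable: LMA power does not move and the false ICS claim rate nearly doubles. This is the real cost. It stays within the family limit the plan adopted, and III.E states the opposite expectation, so the document does not settle which case applies.

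Two practical points also stand. VIII.C uses the same 0.025 rule for the same contrasts in the eosinophilic phenotype, so a p-value of 0.03 could count as positive in one phenotype and negative in the other. And the November 2015 update in Appendix D shows that recruitment was under way, so changing a primary decision rule needs a justified amendment.

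**Conclusion.** The point holds as an improvement in efficiency, not as a correction. Fixed 0.025 tests are valid and deliver the stated power. Holm keeps the same 5% upper limit without any assumption about correlation.

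At the plan's own assumptions (223 evaluable, 30% ties, difference 0.20 for both drugs), the gain is 3 to 4 points per drug and about 6 to 7 points for establishing both. It lies wholly in the second claim. The exact size depends on a correlation that the documents do not give; over the assumed range of 0 to 0.7 the conclusion does not change. The ICS rows at 0.10 and 0.05 in the table rest on the shared-placebo model alone. If only one drug works, there is almost no gain, and the error rate for the other drug's claim rises within the 5% limit.

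**What to change.** Before unblinding, replace the co-primary decision rule in VIII.C with: *The two co-primary hypotheses will be tested with two-sided exact binomial tests using Holm's step-down procedure at family-wise 0.05. The smaller p-value is tested against 0.025 and, only if it is rejected, the larger against 0.05. This rule applies to the co-primary pair only.*

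In VIII.G, add that 0.90 per test at level 0.025 is a lower bound on power per drug under this rule at the stated assumptions. If 97.5% confidence intervals are reported, label them as not being the decision rule, because they will not always agree with the Holm decision.

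The cost is one rule and one clause, issued as a dated amendment that records that treatment results were not known. No participant, visit or data item is added. The sponsor has to accept the mismatch with simple 97.5% intervals, the higher error rate for one drug's claim when only the other works (about 0.02 to 0.037-0.040), and a rule that differs from the one kept for the eosinophilic phenotype.
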